Grade 2 that persists or recurs after resuming the same dose despite maximal supportive measures	Suspend dose until toxicity resolves to ≤Grade 1.
Grade 3 or 4 or requires hospitalization	Resume at next lower dose.

Dose level reductions should be made in 50 mg increments. For example, if the starting dose of abemaciclib for a study is 150 mg q12 hours, dose reduction 1 would be 100 mg q12 hours, dose reduction 2 would be 50 mg q12 hours.

General Guidance for Interstitial lung disease (ILD)/Pneumonitis events

Interstitial lung disease (ILD) / pneumonitis has been identified as an adverse drug reaction for abemaciclib. Adverse events reported included events such as interstitial lung disease, pneumonitis, obliterative bronchiolitis, organizing pneumonia, pulmonary fibrosis. The majority of events were Grade 1 or Grade 2 with serious cases and fatal events reported.

Monitor for clinical symptoms or radiological changes indicative of ILD/pneumonitis and please ask patients to report any new or worsening pulmonary symptoms. Symptoms may include hypoxia, cough, dyspnea, or interstitial infiltrates on radiologic exams.; these symptoms should be investigated and treated as per local clinical practice and/or guidelines (including corticosteroids as appropriate). Infectious, neoplastic, and other causes for such symptoms should be excluded by means of appropriate investigations. Investigations may include imaging such as high resolution computer tomography (HRCT), bronchoalveolar lavage (BAL), and biopsy as clinically indicated (see also Table).

Interstitial Lung Disease (ILD)/Pneumonitis

ILD/Pneumonitis Dose Management Guidelines	
CTCAE Grade	Action
Grade 1-2	No dose modification required
Grade 2 that persists or recurs after resuming the same dose despite maximal supportive measures within 7 days to baseline or Grade 1	Suspend dose until toxicity resolves to ≤Grade 1. Resume at next lower dose.
Grade 3-4	Discontinue abemaciclib

Non-hematological Toxicities (excluding Diarrhea, ALT Increased, and ILD Pneumonitis)

Non-Hematological Toxicity Dose Management Guidelines (excluding Diarrhea, ALT

CONFIDENTIAL

This material is the property of the [UC Irvine Chao Family Comprehensive Cancer Center](#). Do not disclose or use except as authorized in writing by the study sponsor.

Increased, and ILD Pneumonitis)	
Event	Action
Grade 1-2	No dose modification required

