4.4 Concomitant Medications/Treatments

Any medication or vaccine (including over-the-counter or prescription medicines, vitamins, and/or herbal supplements) that the patient is receiving at the time of enrollment or receives during the study must be recorded along with:

- Reason for use
- Dates of administration including start and end dates

CONFIDENTIAL

This material is the property of the [UC Irvine Chao Family Comprehensive Cancer Center](#). Do not disclose or use except as authorized in writing by the study sponsor.

All treatments that the investigator considers necessary for a patient's welfare may be administered at the discretion of the investigator in keeping with the community standards of medical care.

All the concomitant medications and supportive therapy administered during the 30 days prior to the first dose until 30 days after the last dose must be recorded on the appropriate case report form (CRF).

Abemaciclib is predominantly cleared by oxidative metabolism via CYP3A4. Clinical drug interaction studies with a CYP3A inhibitor and CYP3A inducer significantly altered the PK of abemaciclib and its circulating major metabolites.

CYP3A Inducers

Avoid concomitant use of CYP3A inducers and consider alternative agents.

CYP3A Inhibitors

Avoid concomitant use of strong CYP3A inhibitors (for example, voriconazole) and use caution with coadministered moderate (for example, ciprofloxacin) or weak (for example, ranitidine) CYP3A inhibitors. If coadministration with a strong CYP3A inhibitor is unavoidable, reduce the abemaciclib dose to 100 mg twice daily or, in the case of ketoconazole, reduce the abemaciclib dose to 50 mg twice daily. In patients who have had a dose reduction to 100 mg twice daily due to adverse reactions, further reduce the abemaciclib dose to 50 mg twice daily. Avoid grapefruit or grapefruit juice. If a CYP3A inhibitor is discontinued, increase the abemaciclib dose (after 3-5 half-lives of the inhibitor) to the dose that was used before starting the inhibitor

General Guidance for use of Radiotherapy in Combination with Abemaciclib

Limited data are available with abemaciclib and radiotherapy or alternate dosing schedules (e.g. induction phase). Thus, caution should be exercised with administering abemaciclib with radiotherapy.

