4.3.2 Supportive Management for Diarrhea in Patients Receiving Abemaciclib

Patients should receive instructions on the management of diarrhea. In the event of diarrhea, supportive measures should be initiated as early as possible. These include the following:

- At the first sign of loose stools, the patient should initiate anti-diarrheal therapy (e.g., loperamide) and notify the investigator for further instructions and appropriate follow-up.
- Patients should also be encouraged to drink fluids (e.g., 8 to 10 glasses of clear liquids per day).
- Site personnel should assess response within 24 hours.
- If diarrhea does not resolve with anti-diarrheal therapy within 24 hours to at least Grade 1 (per CTCAE v 5.0), study abemaciclib treatment should be suspended until diarrhea is resolved to at least Grade 1.
- When abemaciclib treatment recommences, dosing should be adjusted as outlined in Section 4.2.1. In severe cases of diarrhea, the measuring of

CONFIDENTIAL

This material is the property of the [UC Irvine Chao Family Comprehensive Cancer Center](#). Do not disclose or use except as authorized in writing by the study sponsor.

neutrophil counts and body temperature and proactive management of diarrhea with antidiarrheal agents should be considered.

If diarrhea is severe (requiring intravenous rehydration) and/or associated with fever or severe neutropenia, broad-spectrum antibiotics such as fluoroquinolones should be considered. Patients with severe diarrhea or any diarrhea associated with severe nausea or vomiting should be carefully monitored and given intravenous fluid and electrolyte replacement as clinically indicated.

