APPENDIX C: Inducers and Strong Inhibitors of CYP3A

The information in this appendix is provided for guidance to investigators and does not preclude the use of these medications if clinically indicated

Strong Inducers of CYP3A

Carbamazepine

Rifapentine

Dexamethasone

Rifabutin

Phenobarbital/phenobarbitone

Rifampin

Phenytoin

St. John's Wort

Moderate Inducers of CYP3A

Bosentan

Primidone

Lenisurad

Telostristat ethyl

Modafinil

Strong Inhibitors of CYP3A

Aprepitant

Itraconazole

CONFIDENTIAL

This material is the property of the UC Irvine Chao Family Comprehensive Cancer Center. Do not disclose or use except as authorized in writing by the study sponsor.

Ciprofloxacin	Ketoconazole
Clarithromycin	Nefazodone
Conivaptan	Posaconazole
Diltiazem	Troleandomycin
Erythromycin	Verapamil
Fluconazole	

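### Ciprofloxacin is a moderate CYP3A inhibitor in section 4.4 but a strong one in Appendix C, and the abemaciclib dose depends on the class

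*Combined protocol and SAP*

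**What the plan says.** Section 4.4 (Concomitant Medications/Treatments, under CYP3A inhibitors) sets out what to do by class of inhibitor.

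- Moderate or weak: "use caution with coadministered moderate (for example, ciprofloxacin) or weak (for example, ranitidine) CYP3A inhibitors". No dose change is stated.
- Strong: avoid. Where that is not possible, "If coadministration with a strong CYP3A inhibitor is unavoidable, reduce the abemaciclib dose to 100 mg twice daily". Ketoconazole has its own, lower dose of 50 mg twice daily.
- Strong, after an earlier toxicity reduction: the rule covers those "who have had a dose reduction to 100 mg twice daily due to adverse reactions, further reduce the abemaciclib dose to 50 mg", again as a dose given two times a day.
- When the inhibitor is stopped, the abemaciclib dose goes back to what it was, after 3 to 5 half-lives of the inhibitor.

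Appendix C is titled "APPENDIX C: Inducers and Strong Inhibitors of CYP3A". Under its strong-inhibitor heading, the row "Ciprofloxacin Ketoconazole" puts ciprofloxacin in the list. The appendix opens by stating its status: "The information in this appendix is provided for guidance to investigators and does not preclude the use of these medications if clinically indicated".

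Section 4.3.2 on supportive management of diarrhea adds a setting in which such an antibiotic may be used. For diarrhea that is severe, or that is "associated with fever or severe neutropenia, broad-spectrum antibiotics such as fluoroquinolones should be considered".

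**The concern.** In section 4.4 the inhibitor's class decides the abemaciclib dose, and the protocol gives ciprofloxacin two classes. A prescriber who reads 4.4 would keep the current dose and watch the patient. A pharmacist who looks the drug up in Appendix C and then applies the 4.4 rule for strong inhibitors would object to the combination or ask for a lower dose. Section 4.4 gives examples of inhibitors but no full list, so Appendix C is the natural place to check a drug.

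The error could run either way. If moderate is correct and the appendix is followed, the patient gets less abemaciclib than intended for as long as the antibiotic is given. If strong is correct and 4.4 is followed, the patient has more exposure than the protocol means to allow, possibly while recovering from toxicity.

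**Working it through.** The protocol gives no figure to reproduce. The check sets the two texts side by side and then works out the dose difference.

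**1. Is the mismatch an effect of reading the PDF?** A lost heading for moderate inhibitors could in principle explain it, but two things speak against that. The appendix title covers inducers and strong inhibitors only, so a list of moderate inhibitors would not belong there. The extracted list also reads as two alphabetical columns:

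- left, 7 entries: aprepitant, ciprofloxacin, clarithromycin, conivaptan, diltiazem, erythromycin, fluconazole;
- right, 6 entries: itraconazole, ketoconazole, nefazodone, posaconazole, troleandomycin, verapamil.

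Both columns stay in order across the page break, and ciprofloxacin is second on the left. It belongs to the strong list as printed.

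**2. Largest dose difference while ciprofloxacin is given.** Inputs: starting dose 150 mg twice daily (4.1.1), steps of 50 mg (4.2.1), and the inhibitor rules of 4.4. Daily dose = 2 × single dose.

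- Patient on 150 mg twice daily. Moderate: 2 × 150 = 300 mg/day. Strong: 2 × 100 = 200 mg/day. Difference (300 − 200)/300 = one third.
- Patient already reduced to 100 mg twice daily for adverse reactions. Moderate: 2 × 100 = 200 mg/day. Strong: 2 × 50 = 100 mg/day. Difference (200 − 100)/200 = one half.
- Patient on 50 mg twice daily. Section 4.4 states no further cut, so no difference in dose follows.

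**3. Which case applies in the diarrhea setting.** In the diarrhea table of 4.2.1, the row "Grade 3 or 4 or requires hospitalization" leads to suspension until Grade 1 or lower and then restart one level down. (The action cell appears to be shared with the row above it.)

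- On 150 mg at the event: restart at 100 mg, so the second case above (200 versus 100 mg/day).
- Already on 100 mg at the event: restart at 50 mg, so no stated difference.
- First Grade 2 episode with fever, on 150 mg: no reduction required, so the first case (300 versus 200 mg/day).

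Grade 2 diarrhea that does not settle to Grade 1 within 24 hours also means suspension. Severe neutropenia separately leads to suspension under the hematologic table. After any suspension, a difference arises only if the antibiotic is still being given when abemaciclib restarts.

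**4. What cannot be worked out.** The documents give no rate of ciprofloxacin use, so the number of patients affected cannot be derived.

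**The case against.** The strongest reply is that section 4.4 settles the matter in practice. It holds the only inhibitor dose rules, the sentence stating the rule names ciprofloxacin itself, and it does not send the reader to Appendix C. The appendix calls itself guidance and does not bar the listed drugs. This looks like a wrong entry in an appendix rather than two instructions of equal weight. That stands as a view of where the error probably lies. It does not remove the conflict: the guidance sentence concerns whether a drug may be given, not whether the strong-inhibitor dose then applies, and no sentence gives 4.4 precedence.

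Two further replies hold and limit the size of the point. Use with caution states no cut but does not forbid one, so the contrasts above are upper bounds. In the diarrhea setting abemaciclib will often be suspended when the antibiotic starts. The diarrhea section also names fluoroquinolones, not ciprofloxacin; that ciprofloxacin is one of them is general pharmacology. The contradiction does not depend on that link, since 4.4 and Appendix C both name the drug.

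A reader might infer that any patient with Grade 3 or 4 diarrhea faces the 100 versus 50 mg choice. The documents do not support that: it holds for a patient still on 150 mg at the event, while one already on 100 mg restarts at 50 mg. Nor do the documents establish which class is pharmacologically right.

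**Conclusion.** The point holds as an internal contradiction in the protocol, wrong as written and of low severity. Ciprofloxacin is moderate in 4.4 and strong in Appendix C, and the class decides the dose. The appendix entry is the more likely error, but that is an inference and needs confirming.

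The difference is at most one third of the daily dose in a patient on 150 mg twice daily, and at most one half in a patient already reduced to 100 mg twice daily for adverse reactions. These figures assume that each reader applies the 4.4 rule strictly to the class found, that the combination is in fact given, and that any suspension has ended. The difference is temporary, involves permitted dose levels, and reverses under 4.4 once the inhibitor stops.

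A reader might go on to infer a threat to the primary result. The documents do not support that: inhibitor class enters neither the Simon two-stage design nor the definition or analysis of pCR.

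**What to change.** Ask the drug supplier to confirm ciprofloxacin's CYP3A class first, since the documents do not settle it and removing the entry without checking would choose the higher-exposure option. Then use that one class in both places:

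- if moderate, remove ciprofloxacin from the strong list in Appendix C;
- if strong, replace ciprofloxacin as the example of a moderate inhibitor in 4.4.

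The cost is one query to the supplier and one changed entry at the next amendment, with no added visits, procedures or patients.

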4.2.1 Abemaciclib Dose Modification and Management

Please refer to the following tables for dose modifications for adverse reactions related to abemaciclib. If dose reduction is necessary, decrease the dose by 50 mg at a time. Discontinue abemaciclib for patients unable to tolerate 50 mg twice a day (BID).

Abemaciclib Dose Modifications for Adverse Events

Dose Level	Abemaciclib dose in combination with fulvestrant
Recommended Starting Dose	150 mg
First Dose Reduction	100 mg
Second Dose Reduction	50 mg
Third Dose Reduction	Not applicable

Hematologic Toxicities

Hematologic toxicities including neutropenia, leukopenia, anemia, and thrombocytopenia have been observed in patients treated with abemaciclib, and causality has been established. Severe (Grade 3 and 4) neutropenia was observed in patients receiving abemaciclib. Patients should be monitored closely for signs of infection, anemia, and bleeding.

Hematologic Toxicity Dose Management Guidelines
Monitor complete blood counts prior to the start of abemaciclib therapy, every 2

CONFIDENTIAL

This material is the property of the [UC Irvine Chao Family Comprehensive Cancer Center](#). Do not disclose or use except as authorized in writing by the study sponsor.

weeks for the first 2 months, monthly for the next 2 months, and as clinically indicated.

CTCAE Grade	Action
Grade 1-2	No dose modification required
Grade 3	Suspend dose until toxicity resolves to \leq Grade 2. Dose reduction is not required.
Grade 3, recurrent, or Grade 4	Suspend dose until toxicity resolves to \leq Grade 2. Resume at next lower dose.

If blood cell growth factors are required, suspend abemaciclib dose for at least 48 hours after the last dose of blood cell growth factor and until toxicity resolves to \leq Grade 2. Resume at next lower dose unless already performed for the toxicity that led to the use of the growth factor. Growth factor use as per current treatment guidelines.

Hepatic Toxicities

Alanine aminotransferase (ALT) and aspartate aminotransferase (AST) elevation are considered as ADR with the use of abemaciclib. The following information in Table 3 must be included in investigator-sponsored protocols for hepatic monitoring:

Hepatic Toxicity Dose Management Guidelines	
Monitor ALT prior to the start of abemaciclib therapy, every 2 weeks for the first 2 months, monthly for the next 2 months, and as clinically indicated.	
CTCAE Grade for ALT and AST	Action

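### Section 4.4 returns abemaciclib to its pre-inhibitor dose when any CYP3A inhibitor stops, with no exception for a toxicity reduction made under 4.2.1 after the inhibitor was started

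*Combined protocol and SAP*

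**What the plan says.** Section 4.1.1 starts abemaciclib at 150 mg twice daily. Section 4.2.1 lowers it for toxicity in 50 mg steps to 100 and then 50 mg. For diarrhea, the row "Grade 3 or 4 or requires hospitalization" leads to a hold and resumption one level down. Below the last level the rule is "Discontinue abemaciclib for patients unable to tolerate 50 mg twice a day (BID)".

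Section 4.4 adjusts the dose for CYP3A inhibitors:

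- For weaker inhibitors the site should "use caution with coadministered moderate (for example, ciprofloxacin) or weak (for example, ranitidine) CYP3A inhibitors"; no reduction is given.
- For an unavoidable strong inhibitor the dose falls to 100 mg twice daily, or "in the case of ketoconazole, reduce the abemaciclib dose to 50 mg twice daily".
- For patients who have already had a "dose reduction to 100 mg twice daily due to adverse reactions, further reduce the abemaciclib dose to 50 mg twice daily".
- When an inhibitor is stopped, "increase the abemaciclib dose (after 3-5 half-lives of the inhibitor) to the dose that was used before starting the inhibitor".

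The section headed 4.3.2 Supportive Management for Diarrhea says that for diarrhea not settling within a day "study abemaciclib treatment should be suspended until diarrhea is resolved to at least Grade 1", and that in severe cases "broad-spectrum antibiotics such as fluoroquinolones should be considered". Appendix C, which describes itself as guidance to investigators, lists ciprofloxacin among the strong inhibitors.

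**The concern.** Two rules move the same dose for different reasons. Section 4.2.1 lowers it because the patient did not tolerate it, and section 4.4 lowers it because an inhibitor raises exposure. When the inhibitor goes, only the second reason disappears. The restoring sentence in 4.4 does not separate the two: it names a fixed target, the dose before the inhibitor. If a toxicity reduction was made in between, that target lies above the level that 4.2.1 set.

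At stake is avoidable re-exposure to a higher dose after a Grade 3 event, in patients being treated before surgery with curative intent (section 1.4). Safety and toxicity is a secondary objective (2.2.4). The sentence also leaves no room for judgement, so a site that sensibly keeps the lower dose departs from the text.

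**Working it through.** The plan states no figure to reproduce. The check applies the written rules in order; all doses are mg twice daily.

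**Inputs.** Starting dose 150 (4.1.1). Toxicity step −50 (4.2.1). Moderate or weak inhibitor: no change (4.4). Strong inhibitor other than ketoconazole: to 100, or to 50 if already at 100 for toxicity (4.4). Ketoconazole: to 50 (4.4). Inhibitor stopped: to the dose before it was started (4.4).

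**Dose paths as written**

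| Sequence | Path | Final dose |
|---|---|---|
| A. Moderate inhibitor, then Grade 3 diarrhea, inhibitor stopped | 150 → 150 → 100 → 150 | 150 |
| B. Strong inhibitor (not ketoconazole), then Grade 3 diarrhea, inhibitor stopped | 150 → 100 → 50 → 150 | 150 |
| C. Grade 3 diarrhea, then the same strong inhibitor, inhibitor stopped | 150 → 100 → 50 → 100 | 100 |
| D. Ketoconazole, then toxicity not tolerated at 50 | 150 → 50 → discontinue | none |

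**Size.** In A the toxicity-adjusted level is 150 − 50 = 100, and the rule gives 150. Daily doses are 2 × 150 = 300 mg against 2 × 100 = 200 mg, a ratio of 300/200 = 1.5. B and C have the same starting dose, drug and event in a different order, and end at 150 and 100: again 150/100 = 1.5. Section 4.4 thus keeps a toxicity reduction made before the inhibitor and cancels one made after it. D falls outside the problem, because the patient stops abemaciclib.

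**Does other text close the gap?**

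- 4.2 says to adjust to the system with the worst toxicity, but is silent on raising the dose again.
- 4.2.1 does not call its reductions permanent or bar re-escalation.
- 4.2.2 covers holds and delays only.
- The diarrhea section sends the reader to 4.2.1 when dosing restarts after a hold; it does not govern a later increase.
- The toxicity sentence in 4.4 sets the dose while a strong inhibitor is taken, not the dose after it stops.

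**Ciprofloxacin.** While abemaciclib is being taken, 4.4 (moderate) leaves a patient with no earlier reduction at 150. Appendix C (strong) together with 4.4 gives 100; 150/100 = 1.5. After one toxicity reduction the doses are 100 and 50; 100/50 = 2. During a hold the dose is zero under either text.

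**The case against.** The strongest reply is that the sentence, read in context, only undoes a reduction made for an inhibitor. The paragraph reduces the dose only for strong inhibitors, so with a moderate or weak one there is nothing to restore. That is probably what was meant and how many clinicians would act. It does not settle the matter, since the trigger is any discontinued CYP3A inhibitor and the target is a named dose. It also does not help with sequence B, where a reduction for the inhibitor was made and the literal target still cancels the toxicity step.

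A second reply is that toxicity on an inhibitor may come from raised exposure, so that 150 mg is reasonable once the inhibitor has cleared. This stands for some patients in both A and B. It supports allowing the return as a documented decision; it does not support making it automatic.

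Two stronger readings are tempting and are not supported. First, a reader might infer that ciprofloxacin started during a diarrhea hold is the clearest case, because the event came before any inhibitor. That needs the dose before the inhibitor to mean the last dose taken, 150 mg. It could equally mean the 100 mg level that 4.2.1 already requires on resumption. The antibiotic, or the wait after it, must also extend past resumption, and the protocol suggests only the fluoroquinolone class. It is a possible further example, no more.

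Second, a reader might set 150 against 50 mg and call the rise three-fold. With ciprofloxacin, that needs the contested reading just described, continued use after resumption, and Appendix C overriding 4.4. In sequence B, one of the two steps up properly reverses the inhibitor reduction; the excess is the step from 100 to 150.

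The safeguards also count: checks before each cycle (5.3.1), the 3 to 5 half-life wait, a renewed reduction under 4.2.1 on recurrence, and withdrawal for toxicity or on physician judgement (5.6).

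**Conclusion.** The concern holds as a gap in a written dosing rule. A toxicity reduction made after an inhibitor is started is cancelled when the inhibitor stops, leaving the patient one dose level, or 1.5-fold, above the toxicity-adjusted dose. It does not apply to a reduction made before the inhibitor, or to toxicity not tolerated at 50 mg on ketoconazole.

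This rests on reading 4.4 literally, and on reading the diarrhea table, whose action cells are split in the extracted text, as requiring Grade 3 or 4 events to resume one level lower. The documents give no frequency. Strong inhibitors are to be avoided, and with about 30 patients the sequence is likely to be uncommon. The harm is avoidable re-exposure under continued monitoring, so the priority is low. The Simon two-stage design, its error rates and the pCR endpoint are untouched.

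The ciprofloxacin contradiction is real but separate. The documents do not settle which class is right.

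**What to change.** Reword the restoring sentence in 4.4 along these lines: when a CYP3A inhibitor is stopped, and after 3 to 5 of its half-lives, reverse only the reduction made for that inhibitor, and keep any reduction made under 4.2.1 since it was started. Add a separate sentence for inhibitors of any strength: the pre-inhibitor dose may be resumed if the investigator documents that the toxicity was due to raised exposure on the inhibitor. Keeping this apart from the first sentence matters, because a moderate inhibitor involves no inhibitor reduction and would otherwise have no route back.

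Under this wording A stays at 100 and B returns to 50 + 50 = 100, each with 150 available if documented; C still ends at 100 and D is unchanged.

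Make 4.4 and Appendix C agree on ciprofloxacin. The sponsor should confirm the class; until then, state that 4.4 governs, because Appendix C is labelled guidance.

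The cost is two sentences in 4.4 and one entry in whichever text is corrected, at the next amendment, with no extra patients, visits or tests. The downside is small: some patients whose toxicity was due to the inhibitor may stay on a lower dose unless the decision is documented.
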